Outcome measures Primary outcome: Difference between MLP and KTFS in the change in interpalpebral fissure during and spontaneous blinking

Secondary outcome: Difference between MLP and KTFS in the changes in interpalpebral fissure during opening and volitional blinking

Secondary outcome: Proportion of subjects selecting each device at the end of the crossover

Population: Individuals with severe unilateral or bilateral ptosis defined as occlusion of the visual axis by the lid in the resting state

[figure not shown]
Phase: N/A

Clinical Trial to improve the magnetic levator prosthesis (MLP) including the development and testing of a novel adjustable force system and comparison to the Kinesio Tape frontalis sling (KTFS) Version 1

Number of Sites enrolling participants:	1
Description of Study Agent :	Magnetic levator prosthesis (MLP) with compatible spectacle frames
Study Duration:	Kinesio Tape frontalis sling (KTFS)
Participant Duration:	2 to 3 years
	8 or 9 weeks from enrollment to the end of the crossover period of the clinical trial, with an additional 8 weeks after the end of the crossover for subjects who have a clinical decision to participate in the extended wear part of the clinical trial

SCHEMATIC OF STUDY DESIGN

Also, please refer to the study schema:

FU: Follow up

1 KEY ROLES

Principal Investigator – Overall responsibility for all study related activities.

Co-investigator (clinical trial lead): Responsibility for randomized crossover clinical trial management.

Clinical Research Technicians- Responsible for consenting, enrolling and scheduling subjects. Also will collect, record and report all study data, and fit and train for the MLP device and the tape (KTFS) as a backup plan.

Physical Therapy Advisor: Training of clinical study staff and monitoring the quality of fitting for the KTFS.

Engineering research fellow: Responsible for: Assembling MLP devices and maintaining device logs

Independent safety monitor: Examine participants with adverse events and review all safety outcome reports.

2 INTRODUCTION: BACKGROUND INFORMATION AND SCIENTIFIC RATIONALE

2.1 Background Information

Blepharoptosis, defined as incomplete opening of the upper eyelid, occurs due to abnormalities in the function or structure of the levator palpebrae superioris muscle, injury to or dysfunction of the superior division of the 3rd cranial nerve, or structural abnormalities.[1] Etiologies include congenital

abnormalities, stroke, traumatic brain injury, tumors of the brain or face, viral illnesses, diabetes, autoimmune disorders such as myasthenia gravis, and general aging mechanisms.[1] The prevalence of blepharoptosis within the US general population is unknown; however, in Korean and U.K. general population it has been reported to be 11% [2, 3] suggesting **30 million people in the U.S.** have the disorder.

Severe ptosis and associated ophthalmoplegia cause low vision with negative effects on function and quality of life – Total bilateral ptosis causes profound yet potentially reversible visual impairment. Associated ophthalmoplegia results in an inability to consistently utilize the fovea, and so in many cases magnification is useful. In bilateral 3rd nerve palsy, for example, the eye is frequently permanently abducted 30° or more, so even if the lids are opened common low vision rehabilitation interventions are needed. A similar but usually less severe situation exists in poorly controlled myasthenia gravis. When ptosis is subtotal but severe, patients are symptomatic of constricted visual field reporting problems with mobility and inability to drive. Inability to drive and effort of constant frontalis recruitment limits employability, making travel to work and sustained computer viewing very difficult. Severe unilateral ptosis (CN III palsy) causes loss of binocular peripheral field (~30°), stereopsis, and binocular summation (which is often problematic at night or other dim environments). All levels of ptosis have negative social and cosmetic impacts which are likely to affect employment and social well-being.

Common surgical treatments - The most common method currently used to correct ptosis involves surgical tightening of the levator muscle, or in more severe cases, frontalis sling.[1] While these procedures are a mainstay of treatment, in our experience they have disadvantages in that they do not always restore normal blink function and over-correction may result in exposure keratitis. In severe cases of ptosis a conservative approach is needed leaving the ptosis under-corrected, and so even surgical candidates may benefit from magnetic correction.

An effective easily adjustable and/or non-surgical treatment is needed - Substantially less attention has been given to non-surgical approaches for ptosis, which has led to lack of effective options during the early recovery period from neurological etiologies, in cases with daily variability in the ptosis such as Myasthenia Gravis, or other cases where surgery is contraindicated. Ability for the patient to easily adjust the correction as the ptosis varies would be advantageous whether it were applied surgically or not.

Limitations of available temporary treatments - We believe that available temporary or non-surgical treatments are ineffective and even contraindicated for many target populations. These include taping the lid(s) open and propping the lid open with a wire on the glasses (ptosis crutch).[4] Unfortunately there is a paucity of data on safety or efficacy of the ptosis crutch or taping. The crutch has to be continually adjusted to keep the lid elevated, does not allow a complete blink,[5] and poses a risk for ocular injury during adjustment or should the patient fall. We have frequently encountered use of skin tape to elevate the eye lid, but this has potentially damaging effects on the ocular surface from incomplete eye closure. A newly released eye drop (Upneeq, Osmotica/RVL, January 2021) has recently been approved for mild age-related ptosis (might be used off label for severe myo or neurogenic ptosis), but its effects are unknown for severe ptosis.

Static magnets could provide force to elevate the eyelid while still allowing eye closure - In most types of ptosis, while opening of the eyelid is impaired, the neuromuscular complex for eye closure (Orbicularis oculi muscle/cranial nerve (CN) VII) is intact. [1] In these cases the ptosis might be alleviated using a permanent static magnet system to provide the force to elevate the upper eyelid.[6] The static force exerted by the permanent magnet to open the eyelid should be easily overcome by the Orbicularis Oculi muscle, assuming the force of the magnet is not too great, reanimating the blink. This approach utilizes well-understood, widely available and inexpensive static magnetic materials. Electromagnets might seem like an attractive option for the ability to modulate force; however, they generate heat and would consume too much energy to be feasible for continuous use. We had also considered electrical

stimulation of the levator muscle; however, our mentors who have investigated the possibility of this approach previously indicated that repeated stimulation externally on the skin is painful in addition to difficulty accessing the levator non-surgically via this technique.

Prior attempts to use magnets for ptosis - The concept of correcting ptosis with magnetic force was first presented in the 1970's.[6] Conway described attaching Mu-metal 13 x 4 x 0.5 mm to the upper lid in 3 patients (attached with eyelash adhesive or bladerm tape), and a small bar magnet to the spectacles. Specifications of the ferrite spectacle magnet were not provided; however, we measured them in the photos to be ~20 x 5 x 10mm. Conway's photographs showed elevation of the eyelid when the lid and spectacle magnet were in contact; however, the ferrite magnet/Mu-metal would not have generated enough force to elevate the lid from the closed position, where there is typically 15 to 20mm separation.[5] As a result the magnet glasses would have needed frequent adjustment to bring the materials back into direct contact after each blink offering no substantial benefit over the long available ptosis crutch. It is therefore not surprising that the treatment was never commercialized. Since Conway's report, we find no publications on the use of magnets for ptosis, although they have been attempted for lagophthalmos via surgical implantation with only limited success.[7-10] Problems related to surgical implantation highlight the benefit of first refining the approach non-surgically. Static magnets are also better suited for ptosis as compared to lagophthalmos, because of the relative strength of the orbicularis compared to the levator.

2.2 Rationale

We recently described a novel non-surgical magnetic eyewear device referred to as the **Magnetic Levator Prosthesis (MLP)** that restored blinking in patients with severe paralytic ptosis.[5, 17-19] The force to lift the lid was produced by a static Neodymium magnet embedded in a glasses frame and a polymer embedded (PDMS) micro-magnet array fitted externally to the upper lid with Tegaderm IV securement film (Fig 1). The Tegaderm is FDA approved for extended wear on the skin and even as an eye covering. It generated a strong bond, keeping the magnetic array affixed to the eye lid skin for a mean of 6 ± 4 days with good patient reported comfort when used for 2 hours per day during rehabilitation therapies.

Translational Promise – This proposed research to further improve the approach and confirm safety, feasibility, and relative efficacy for chronic management of ptosis is needed prior to commercialization. The aims of the proposed study target the clinical population of the PI who specializes in low vision rehabilitation with subspecialty in neurological visual impairments. This is a large and underserved patient population which includes many individuals with recent neurological pathology, many of whom are residing in inpatient rehabilitation facilities (IRF). IRFs provide 24 hour medical supervision and rehabilitation therapies to patients who are medically stable and are able to participate in a minimum of 3 hours/day of therapy. There are 1,165 IRFs in the U.S.[20] with an average length of stay of 16 days.[21] If we conservatively estimate an average of 50 beds per 1,165 IRFs revolving every 16 days there should be approximately 1.2 million admissions and discharges per year in IRFs nationwide. Of that population, ~32% are recovering from stroke and 6% from traumatic brain injury.[21] Prevalence of CN III palsy in stroke populations has been reported at 2.5%,[22] and 4.4% in TBI (internal data). Therefore, the estimated national target population for temporary management of severe ptosis in IRFs alone is 12,000 patients annually. In our IRF, internal review found a rate of 24 cases of severe ptosis in 2015-2016. No one stands to directly and immediately benefit more from this technology than patients with severe bilateral ptosis. While this is presumed to be a rare situation we have encountered 8 such patients in the past 2 years without any active recruiting effort. We have also encountered multiple patients with severe unilateral ptosis obscuring the vision in their better eye for whom surgery was contraindicated. There is no available option for these patients other than taping the lids open or the ptosis crutch with the aforementioned problems with these approaches.

Scientific Premise: In summary, the premise for the proposed work is that ptosis is a major public health concern which to this point has received less attention than its lagophthalmos counterpart despite the fact that it causes similar discomfort and disability (but without the extreme consequence of exposure and scarring). Better non-surgical options are needed. Weaknesses in prior work in the field concerning magnetic correction included use of ferrite magnets, inadequate adhesion methods for external placement, moving too soon to surgical implantation, and lack of evidence from randomized controlled trials to guide clinical approaches. We will fill a significant gap in the field in terms of non-surgical correction while not excluding use of data and methodology to advance success with surgical implantation. In the first part of this study the magnetic levator prosthesis (MLP) was improved by development and testing of a novel adjustable force system and in the second part of the study the MLP will be compared to another non-surgical treatment for blepharoptosis, the Kinesio Tape frontalis sling (KTFS)

Risk 2, reduced blink reflex: If the fitting of the MLP is not ideal, it is possible that participants (children and adults) would experience slowed or incomplete blink reflex. There is the potential that this could cause reversible ocular surface drying and discomfort. Participants, parents, and involved caregivers will be given specific instruction on how identify problems and when to remove the MLP. To summarize, they will be instructed to ask themselves at regular intervals “what is my level of comfort on a scale of 1-10” and if it is lower than 5 to remove the MLP and contact the study staff to schedule a visit to investigate. It is also possible that a reduced blink reflex could elevate the risk of foreign body in the case of projectiles. All participants will be fitted with safety grade or polycarbonate lenses, in their prescription (or non-prescription plano if they require none). Participants will be instructed to wear additional protective eyewear and to avoid places like machine shops where there could be metal shavings. The lid magnets are not strong enough to propel a magnetic/metal object towards the eye and the magnets should actually reduce the risk for metallic foreign body projectile entering the eye by redirecting it towards the spectacle magnet; however, there is risk that metal shavings could accumulate around the magnets if the device is

Clinical Trial to improve the magnetic levator prosthesis (MLP) including the development and testing of a novel adjustable force system and comparison to the Kinesio Tape frontalis sling (KTFS) Version 1

used in a situation such as a workshop where shavings are present. While these would not be projected into the eye, minor injury may result if the shavings get around the eye and then are rubbed into or sprinkle into the eye(s). Standard safety goggles will fit over the spectacles and participants will be informed that they should be worn as they normally would.

Risks related to KTFS taping:

Kinesio Tape is FDA registered with an indication for extended use on the skin. Clinically it is most often used on the upper extremities to support sore or injured muscles. It is also often used on the face for facial palsy [7], and sometimes on the eye lids for blepharoptosis. It is easily removed without any special tools or procedures. Similar to the MLP, there is the possibility that participants might experience ocular surface drying and discomfort. There is also a possibility of skin irritation from the tape. Participants, parents, and involved caregivers will be given specific instruction on how to identify problems and when to remove the tape.

2.3.2 Known Potential Benefits

Possible treatment for restoration of eyelid motility in subjects who wear the device comfortably.

3 OBJECTIVES AND PURPOSE

To provide a higher level of evidence for the MLP as an emerging treatment, and to determine barriers to displacing current non-surgical and temporary approaches.

To improve the magnetic levator prosthesis (MLP) by development and testing of a novel adjustable force system. If endpoints are met and the device is determined to be feasible the study will continue to a randomized clinical trial comparing the MLP against the predicate treatment of taping the lids.

4 STUDY DESIGN AND ENDPOINTS

4.1 Description of the Study Design

The study is a double-blind, randomized crossover clinical trial comparing two non-surgical treatments, the MLP and KTFS, for blepharoptosis. After the end of the crossover, there will be an optional extended wear period in which participants may be invited to continue using the preferred device for up to another six months, if clinically appropriate.

4.2.1 Primary Endpoints

A difference between MLP and KTFS of at least 1mm in the change in interpalpebral fissure during opening and spontaneous blinking.

5 STUDY RECRUITMENT, ENROLLMENT AND WITHDRAWAL

Patient Gateway for recruitment will be utilized.

5.1 Participant Inclusion Criteria:

1. Presence of Blepharoptosis for at least one eye which occludes the visual axis in the resting state (no frontalis drive),
2. Moderate cognitive function or better defined as greater than or equal to 18 out of 30 on a pre-screening of the Mini-Mental State Exam.

3. Age 5 or older. (Children need to be included because they represent an important target population (pediatric neuro-muscular conditions), and because facial structure and skin characteristics may result in a different response than adults)

5.2 Participant Exclusion Criteria:

1. Absence of ptosis which occludes the visual axis
2. Presence of a corneal ulcer of any size, unless managed with a protective contact lens or other method and permission is granted from the candidate's managing eye doctor.
3. Age less than 5,
4. Severe Cognitive impairment defined as MMSE score <18, behaviors consistent with delirium (combinations of disorientation, hallucinations, delusions, and incoherent speech), or lethargy.
5. Presence of corneal hypoesthesia unless cleared for enrollment by a cornea or contact lens specialist;
6. Orbicularis weakness on the side of the ptosis.
7. Mechanical ptosis, including ptosis due to orbital or lid tumor, cicatricial processes affecting the movements of the upper lid, and exophthalmos.
8. Previous ptosis surgery less than 3 months prior to Visit 1.
9. Lid position affected by lid or conjunctival scarring.
10. History of herpes keratitis.
11. Periocular neurotoxin (eg, Botox, Xeomin, Dysport, Myobloc) injections on the side of the ptosis within 3 months prior to Visit 1 and during the study.
12. History of hyperthyroidism or thyroid eye disease (ie, exophthalmos, upper eyelid retraction, diplopia secondary to extraocular muscle involvement). Hypothyroidism that is controlled on medication is allowed.

Hypoesthesia and chronic corneal ulcers may be treated successfully, usually with artificial tears and/or a protective contact lens. Therefore, when there is hypoesthesia or chronic epithelial defect the PI will contact the candidate's cornea or contact lens specialist (e.g. via email or EMR message (EPIC)), and request permission to enroll the candidate. If they do not have a cornea or contact lens specialist, a consult with one at MEE who is not affiliated with the study will be requested prior to enrollment.

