7 STUDY PROCEDURES AND SCHEDULE

7.1 Study Procedures/Evaluations

7.1.1 Study specific procedures

The following procedures will be performed as part of the study (see schedule of events table in section 7.3.7.)

1. Refraction (if needed)
2. Visual acuity
3. Slit lamp examination of external eye, lid and cornea with Nafl & NEI scale
4. Comfort rating
5. Video recording of eye blinks
6. Rating of skin integrity
7. EQ-5D-5L questionnaire
8. GBI questionnaire
9. aQoL questionnaire

Based on experience, we anticipate that the first study visit will typically last about 120 minutes and subsequent visits about 60 minutes.

Some of the visits will be conducted virtually (as detailed in subsequent sections). To facilitate virtual visits, a visual acuity chart will be given to the subject to allow this safety outcome monitoring remotely and other safety outcomes will be conducted during the call (comfort scale, inspection of the external eye and lid skin).

Detailed plan for REDCap text message and email communication:

A short three-question survey will be used to document whether subjects are wearing a device during the periods of home use. Consent to receive a survey link by text message or email will be documented in the consent form along with the preferred contact method (text, email, or both). For subjects that consent to receive the survey links, their preferred phone number and/or email address will be recorded on a sheet separate from the consent form, which will be kept in a locked cabinet in a locked office. As soon as the phone number and/or email address have been input into REDCap, the original will be shredded.

Subjects who consent to receive the survey links will receive a text message or email (based on their communication preference) with a link to a REDCap survey twice daily when using one of the devices at home during the trial week. Please see uploaded document for details of the survey language and questions. Subjects will be able to decline receiving the survey links at any time.

Text message plan: Text messages will be sent to subjects using the Twilio platform. The “Survey as webpage” option will be selected so that subjects can access the REDCap survey URL directly from the text. Subjects’ phone numbers will only be entered if they consented to receiving messages in this way. A sentence in the text message will notify the subject that they can opt out of receiving these texts by replying “Stop”.

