7.3.2 CROSSOVER

After consent and enrollment, subjects will be randomly assigned to one of the two arms for the crossover period. In one arm subjects will receive the MLP first and the KTFS second. In the other arm, subjects will receive the KTFS first and the MLP second.

Each period of the crossover will last for about three weeks, including about two weeks of training in how to apply and remove the device followed by about one week of using the device at home. Training will be conducted at study visits at Mass Eye and Ear. Typically there will be two training visits. Baseline measures of eye lid blinking without and with the device will be taken during training. For the MLP, two baseline measures of eye lid blinking will be recorded one with the real MLP device and one with a sham MLP device to determine how much improvement might occur simply through a placebo effect. However, for the KTFS it will not be possible to take a baseline measure with a sham KTFS. Only subjects and caregivers who demonstrate sufficient ability to apply and remove the device will be permitted to take it home. During the period of home wear, there will be a video call every other day to monitor the subject’s use of the device and safety. During the kfts arm, an occupational or physical therapist consulting with the Massachusetts eye and ear study team may talk with the subject during the video conference call to ensure that the kinesio tape is in the correct position. Mass General Brigham approved software will be used for video calls. During the trial week of home use of devices, subjects will

also receive REDCap survey link notifications each day to complete a brief survey to log if they are wearing the device (see the detailed plan above, and see attached document for survey language and questions).

To ensure no carry-over effects, there will be a washout of about 2 weeks duration between the first and second period of the crossover during which subjects will not be permitted to use any device for their blepharoptosis. (This will be similar to their habitual state before enrollment since none of the participants would have been using any device for their blepharoptosis about two weeks before enrollment).

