7.3.7 Schedule of Events Table

*Visits 8-10 are in office, approximately every second week. There will be video

		Consent	EQ-5D-5L Questionnaire	aQoL Questionnaire	GBI Questionnaire	Visual Acuity	SlitLamp, skin rating, & NEI grading	Video Recordings & Comfort ratings	Application & Removal training	Debrief and device comparison questionnaire	Clinical decision
Device 1	Visit 1	x	x	x		x	x	x	x		
	Visit 2					x	x	x	x		
		About 1 week wearing at home with video calls for safety monitoring and daily survey about wear time									
	Visit 3		x	x	x	x	x	x			
	Washout (about 2 weeks)										
Device 2	Visit 4		x	x		x	x	x	x		
	Visit 5					x	x	x	x		
		About 1 week wearing at home with video calls for safety monitoring and daily survey about wear time									
	Visit 6		x	x	x	x	x	x			
	End of crossover period										
	Phone call									x	
	Visit 7					x	x	x			x
	Start of extended wear trial (about 6 months)										
Chosen device											
	Visit 8		x	x	x	x	x	x			
	Long term follow up										
	6 month phonecall		x	x	x						
	12 month phonecall		x	x	x						

call follow ups on weeks without an in-office visit

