8 ASSESSMENT OF SAFETY

8.1 Specification of Safety Parameters

The safety of the study devices will be evaluated at every visit following the enrollment visit and will be defined by the incidence of related adverse events. Specifically, we will evaluate:

10. **Systemic safety:** Incidence and severity of systemic adverse events during the study (adverse events spontaneously reported or observed by the Research Assistant).
11. **Ocular safety:** Incidence and severity of ocular adverse events during the study (ophthalmic examination, adverse events spontaneously reported).

SAFETY CUTOFFS: Serious adverse events which would result in study suspension: Should visual acuity decrease more than 2 lines, worsening of corneal rating of more than 1.5 points or other ocular surface ratings more than 2 points, and comfort rating lower than 5/10; study activities will cease for at least 1 week and an adverse event report will be sent to the IRB. Corneal rating changes >1.5 points will be reviewed by the independent safety monitor at the Eye and Ear to determine if criteria for study suspension or dismissal are met, and when it may be possible to continue. Serious adverse events which will result in immediate dismissal from the study (and treatment) include: 1) development of a related corneal ulcer (as judged clinically by the independent safety monitor) with or without infiltrate or 2) broken skin on the eyelid (skin decompensation).

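### Participants with corneal hypoesthesia may be cleared to enroll, but the one removal criterion stated for them to apply at home (MLP only) is a comfort score that reduced corneal sensation can blunt

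*Combined protocol and SAP*

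**What the plan says.** **Eligibility.** Section 5.2, exclusion 5, reads "Presence of corneal hypoesthesia unless cleared for enrollment by a cornea or contact lens specialist". The paragraph after the list explains that the condition can usually be treated with artificial tears or a protective lens. It sends the decision to the candidate's own specialist, or to one outside the study. It adds no home monitoring for those admitted.

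**MLP, participant's own rule.** Under Risk 2 (reduced blink reflex), just before section 2.3.2, participants, parents and caregivers are promised instruction on spotting problems. The protocol then summarizes it: rate comfort from 1 to 10 at regular intervals, "and if it is lower than 5 to remove the MLP and contact the study staff".

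**KTFS, participant's own rule.** The paragraph on taping risks says that participants, parents and caregivers "will be given specific instruction on how to identify problems and when to remove the tape". It gives no sign, symptom or threshold.

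**Staff-applied safeguards.**
- Section 7.3.2: during home wear "there will be a video call every other day to monitor" device use and safety.
- Section 7.1.1: participants receive an acuity chart for remote checks, and "other safety outcomes will be conducted during the call (comfort scale, inspection of the external eye and lid skin".
- Section 8.1: cutoffs for acuity, corneal rating, other ocular surface ratings and comfort lead to a pause of a week or longer. In addition, "Corneal rating changes >1.5 points will be reviewed by the independent safety monitor".
- Section 7.3.7: slit-lamp examination and corneal grading take place at visits.
- Section 7.10: virtual participants need a recent complete eye exam. They are sent corneal sensitivity supplies, a Burton lamp and fluorescein strips.
- Sections 1 and 10.4.4: the independent safety monitor examines participants with adverse events, and the investigator reviews magnified images of the ocular surface.

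**The concern.** Drying of the ocular surface is a named risk of both devices. Section 2.1 says of ordinary skin tape used to lift the lid, without naming Kinesio Tape, "but this has potentially damaging effects on the ocular surface from incomplete eye closure". Section 8.1 makes a device-related corneal ulcer a reason for immediate dismissal, so the protocol foresees the serious end of this pathway.

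A comfort score works as an alarm only if the eye reports discomfort. A participant with reduced corneal sensation could keep scoring 5 or more while the surface deteriorates, follow the stated rule correctly, and leave the device on until the next contact. Redness, discharge and worsening vision do not depend on corneal sensation, and a caregiver can see the first two. That matters in a trial that enrolls children from age 5 and adults with MMSE scores of 18 to 23.

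**Working it through.** The documents give no figure to reproduce. The check has two parts: which triggers depend on sensation, and how long the intervals are in which the participant's own rule stands alone.

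**1. Triggers side by side**

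| Trigger | Applied by | Depends on corneal sensation? | Device |
|---|---|---|---|
| Comfort below 5 (Risk 2) | Participant | Yes | MLP |
| Removal instruction, content not stated (taping risks) | Participant | Unknown | KTFS |
| Comfort below 5/10 (8.1) | Staff | Yes | Both |
| Acuity loss of more than 2 lines (8.1) | Staff | No | Both |
| Corneal rating worse by more than 1.5 points (8.1) | Staff | No | Both |
| Other surface ratings worse by more than 2 points (8.1) | Staff | No | Both |

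Triggers that do not depend on sensation therefore exist for both devices, but all of those written down are applied by staff. Section 8.1 pauses study activities rather than telling a participant to remove a device. It also joins its criteria with 'and', so it is unclear whether one is enough.

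**2. Crossover home wear (7.3.2, 7.3.7)**
- Home period: about 7 days, with a call every other day.
- Calls per period: 3 (days 2, 4, 6) to 4 (days 1, 3, 5, 7).
- Two periods: 2 × 3 = 6 to 2 × 4 = 8 calls.
- Gap between contacts: about 2 days.
- Corneal gradings: Visit 2 to Visit 3, and Visit 5 to Visit 6, each about 7 days apart. In-person participants have no fluorescein examination scheduled in between.

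**3. Extended wear (7.3.3, 7.3.7)**
- Section 7.3.3 states a visit each month and mentions no calls. Gradings are then about 30 days apart.
- The note to the 7.3.7 table places office visits about every second week, with video "call follow ups on weeks without an in-office visit". Gradings are then about 14 days apart and contacts about 7 days apart.
- If the note's calls are added to the monthly visits of 7.3.3, contacts are still about 7 days apart and gradings about 30.
- The two sources do not agree. The note speaks of Visits 8-10, but the table lists only Visit 8. Three visits at two-week intervals span about 3 × 2 = 6 weeks. That is nearer the 8-week extension in the Protocol Summary than the six months in 4.1 and 7.3.3.

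The 2-day figure is therefore firm. The 7-day figure assumes that the note applies throughout extended wear.

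**The case against.** The strongest reply is that the gap may not exist. The MLP rule is introduced as a summary of fuller instructions, and the taping paragraph promises its own. Neither the instruction sheet nor the text directly before Risk 2 was available. This stands: 'only' means only in the text that could be read, and the KTFS half on its own is no more than missing detail.

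A second reply is that the risk is already managed. A specialist must clear each case, calls come every other day, acuity and the external eye can be checked remotely, and section 8.1 sets cutoffs for both devices. Extended wear is limited to participants for whom the study doctor finds it appropriate, and that doctor may ask for more frequent visits. This also stands, and it confines the point to the time between contacts. It does not remove it, because clearance happens once at entry and the other measures wait for a contact.

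A reader might infer more, and the documents do not support it:
- That comfort is the only stop trigger during home wear, or that KTFS has none. Section 8.1 covers both devices and includes acuity, which can be tested at home.
- That participants in extended wear go a month without contact. Section 7.3.3 read alone could suggest this, but the table note adds calls.
- That the primary comparison is biased. Nothing in the documents links this gap to the fissure measurements.

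**Conclusion.** The point holds as a minor safety gap. The plan knowingly admits participants with reduced corneal sensation, and the one home-removal criterion it states for participants to apply themselves relies on sensation. Exposure is limited to about 2 days at a time in crossover home wear. In extended wear it is longer, and the schedule is stated inconsistently.

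This rests on three assumptions: that the unseen instructions do not already contain a sign-based rule, that home-week calls include the remote checks of section 7.1.1, and that some participants with hypoesthesia enroll. The documents give no count, and it may be zero. They give no event rate either, so no expected number of harms can be stated. Confidence is medium.

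**What to change.** In the Risk 2 paragraph (MLP) and the taping-risk paragraph (KTFS), and on the participant instruction sheet if it does not already say so, add:

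> Participants with corneal hypoesthesia at enrollment, or their caregiver, will look at the eye at least daily during home wear and will remove the device and call study staff the same day for new or increased redness, discharge, or worsening of vision in the treated eye compared with its vision when the device was fitted, whatever the comfort score.

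The vision clause is tied to the vision at fitting because entry requires a lid that blocks the visual axis. Lifting that lid is meant to change vision, so an unanchored clause could fire on the intended effect.

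**Cost.** One sentence in two places, plus the sheet if needed. Sensation status must already be known to apply exclusion 5, and virtual candidates are mailed the testing supplies. No scheduled visits or participants are added. The downside is some extra calls and removals, which could shorten home wear before the 1-week measurement (section 10.4.2) for an affected participant.
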